Appendix 10.3: Instruction to Subjects

Preliminary Content for General Instructions To Subjects

1 General Instructions Prior to Visit 1

All subjects are responsible for picking up their 24-hour urine specimen collection vessel before Visit 1, Day 1. Upon return to the central facility on Visit 1, Day 1, the subject is required to bring back the urine specimen collection vessel, having filled it over the previous 24-hour period.

Subjects also will be instructed before Visit 1, Day 1 to bring the name and contact information of their family physician. On the Adult Consent Form/Information Sheet and the Parent or Guardian Consent Form/Information Sheet, subjects are given the option to provide this information should they want their medical test results, or those of their children, forwarded to their family physician. Therefore, subjects should have their physician's name and telephone number on hand for Visit 1, Day 1.

2 Instructions for Urine Collection over 24-Hour Period

To ensure the most accurate reading of the urine specimen, special care must be taken in its collection. Please note the following:

- Be advised that there are potentially hazardous preservatives within the collection container.
- Discard the first morning specimen and record this time of voiding.
- Collect all subsequent voided urine for the remainder of the day and night.
- Collect the first morning specimen on day two at the same time as noted on day one.

3 Instructions for T.R.U.E. (Thin-layer Rapid Use Epicutaneous Test)

3.1 Instructions Prior to Visit 1, Specific to T.R.U.E.

Before you have the patch test performed (Visit1), you should:

- NOT consume seafood (i.e., shellfish)
- NOT apply topical corticosteroids (e.g. hydrocortisone) to the patch test area (your back) for one to two weeks before your test date (Visit 1);
- NOT take oral corticosteroids at a dose equivalent to or greater than 15 mg of Prednisone within one week of your test date (Visit 1);
- NOT take an injectable corticosteroid within one month of your test date (Visit 1);
- NOT take oral cyclosporin within one week of your test date (Visit1);
- NOT apply lotions, creams or ointments to the test area before the test (Visit 1);
- Minimize sun exposure to the test area before the test (Visit 1).

Note: Excessive back hair may have to be shaved before patch testing to allow for adhesion of the test strips.

At the time of your first visit (Visit 1, Day 1), you must NOT:

- Have dermatitis on the patch test site, or any other inflammatory skin condition e.g. psoriasis, sunburn; or
- Be pregnant.

Note: If the tape strips become loose, you should have them re-attached at home with an extra piece of tape.

3.2 Instructions for T.R.U.E. Post-Application, Given to Subject before Departure

Note: The subject will be given written as well as verbal instructions concerning the care and protection of the test strips.

During the testing period (96 hours), you must:

- Keep the patch test area dry. Avoid activities that cause perspiration (e.g. exercise, manual labour) and do NOT take a shower until after the final visit (Visit 3, 96 hours after application of patch). You may take a shallow bath as long as you can keep your back dry;
- Wear loose clothing; and
- Call the facility immediately if the test site itches or burns severely.

You may develop itching under the patches. If itching occurs and becomes severe or painful, you should contact the facility, or carefully remove the painful patch yourself.

For the first day, the tape may feel tight. After the strips are removed, your back may feel sticky. During the two days that you wear the patches, you may experience some itching, but most people have little difficulty. One or more test spots may become itchy. These

areas may be red and swollen or sometimes oozy when the tests are removed at 48 hours.

This reaction may increase over the next few days.

The results of your patch testing will be given to you along with an information sheet that explains the meaning of a positive test(s).

At least 72 hours is necessary for allergic reactions to develop fully and for some irritant reactions to subside.

The p-phenylenediamine site may turn black. This is because the allergen is a dye; it does not represent an allergic reaction. This discoloration may remain for up to four weeks.

Side Effects:

1. If in the past, you have experienced an allergic rash to one of the tested substances, your skin rash may recur (“wake up”) if you develop a positive reaction to the substance during the patch testing procedure.
2. Uncommonly, reactions may persist a few weeks. They can be treated with cortisone creams.
3. As they heal, positive reactions at the test sites may sometimes leave brown or white spots on the skin. Most of these marks will fade slowly over time but on occasion may be permanent.
4. Rarely, a positive patch test site may become infected.
5. A person with psoriasis may develop psoriasis at the site of a positive patch test.

6. Very rarely, people may develop an allergy to a substance used in the tests. This usually appears as a positive reaction two to three weeks after the tests.
7. Extremely rarely, a systemic reaction may appear within one hour of a substance being applied on the skin.

Subject Return Visit Schedule:

	Visit 1 (Day 1)	Visit 2 (Day 3)	Visit 3 (Day 5)
Hour	0	48	96
Step	Application of Patch	Removal of Patch	Scoring of Site
Subject Appointments	Date: _____ Time: _____ Initial: _____	Date: _____ Time: _____ Initial: _____	Date: _____ Time: _____ Initial: _____

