4.1.1.1.2 Exclusion Criteria

Participants will be excluded from the study if they cannot comply with the study procedures.

Participants may not be included in the skin sensitivity assessment if they:

1. Have had topical corticosteroids applied to patch test sites within 24 hours of the test date,
2. Have taken oral corticosteroids at a dose equivalent to greater than 15 mg of prednisone within one week of test date,
3. Have had injectable corticosteroid within one month of testing,
4. Have taken oral cyclosporine within one week of testing,
5. Have one or more patch test sites not free of dermatitis, or any other inflammatory skin condition (e.g. psoriasis, sunburn),
6. Are pregnant,
7. Are not available for the application or reading of the patch tests, or

8. Cannot keep the dermatological patch test dry for 96 hours (this includes keeping the test sites free of excessive perspiration that may effect the outcome of the test or cause the patch to detach from the skin).

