4.2.3.3.1 Skin sensitivity assessment

Prior to dermatology testing, subjects will have filled out the health questionnaire which contains dermatology questions that will be used to obtain information concerning dermatological points of interest including questions about jewelry that pierces the skin and the possible presence of atopic dermatitis. A standardized ready to use patch test system, the TRUE test, will be employed (Brasch et al 2001; Suneja and Belsito 2001). This system has been found to be at least as comparable in terms of accuracy and reproducibility, to the conventional Finn Chamber technique of patch testing in its detection of nickel and cobalt allergic individuals (Suneja 2001, Golhausen 1989).

A group of trained study nurses will perform all patch test administration, including application and removal. Patch test scoring will be carried out by a smaller group of specially trained study nurses to maintain high inter-rater reliability. Patch tests will be applied on the upper back. Their edges will be marked with a hypoallergenic marker. Patch tests will remain on the skin for a period of 48 ± 2 hours. During this time, subjects will be given written instructions on test compliance (see Appendix 11.3 for more information). Following this, patch tests will be removed by a trained nurse. Skin sensitivity will be scored 48 hours following removal of the patch test (at 96 hours).

Patch test responses will be scored as either negative, or positive. A positive patch test result is interpreted as a 1+, 2+ or 3+ reaction. This interpretation is based on the following scale (ICDRG 1984): a) 1+ = diffuse confluent erythema with palpable infiltration; b) 2+ = erythema and infiltration with papules and discrete vesicles; and c) 3+ = spreading strong erythema and infiltration with coalescing vesicles/bullous reaction and / or crust with ulceration. Irritant reactions (weak, macular erythema without infiltration or a follicular (pore) pattern restricted to the area covered by the patch) are not regarded as positive and are denoted as “IR”.

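### The take-home patch-test sheet allows unrecorded home removal, and the bars on corticosteroids and creams stop at Visit 1, so a true reaction could be blunted before the 96-hour reading without anyone knowing.

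*Protocol*

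**What the plan says.** **Contact and removal.** Protocol Section 4.2.3.3.1 states: "Patch tests will remain on the skin for a period of 48 ± 2 hours". A trained nurse then removes the patch, and Section 4.2.4.3 (Visit 2) repeats this. The sheet given at departure (Appendix 10.3, item 3.2) lists among the things a participant must do: "Call the facility immediately if the test site itches or burns severely". Its next paragraph offers a choice: "If itching occurs and becomes severe or painful, you should contact the facility, or carefully remove the painful patch yourself".

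**Corticosteroids and creams.** Section 4.1.1.1.2 keeps from skin testing those who "Have had topical corticosteroids applied to patch test sites within 24 hours of the test date". Appendix 10.3, item 3.1, bars topical corticosteroids on the back for one to two weeks before Visit 1, and bars lotions, creams and ointments on the test area before Visit 1. The list for the 96-hour test period covers dryness, perspiration, showering, loose clothing and calling the facility. It does not mention creams or corticosteroids. Of a site that is red, swollen or oozing at removal, the sheet says: "This reaction may increase over the next few days". Under side effects it adds: "Uncommonly, reactions may persist a few weeks. They can be treated with cortisone creams".

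**Reading.** The site is scored at "Visit 3, 96 hours after application of patch". Section 4.2.3.3.1 scores a response as negative or positive. A 1+ needs palpable infiltration, and weak macular erythema without infiltration counts as irritant, not positive.

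**The concern.** A participant who follows the sheet exactly can shorten the contact time at home, or put a steroid cream on a developing reaction before it is read. Neither event is asked about in the visit descriptions. Either could reduce a true allergic reaction below the palpable infiltration that a 1+ requires. The people most likely to remove a patch or treat a site are those who are reacting, so any error would fall mainly on true positives and lower the measured prevalence.

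Nickel sensitivity in women is one of the two outcomes on which the sample size rests (Section 6.1.1). Section 3.2.2.5 also uses the patch tests to validate the contact dermatitis question. Removal time and site treatment cannot be reliably recovered once Visit 3 is over.

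**Working it through.** The protocol gives no rate of self-removal or treatment. The check is therefore a comparison of the texts, followed by an illustration of size.

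**Step 1: removal.** Nurse removal at 48 ± 2 hours sets a lower contact limit of 48 − 2 = 46 hours. The sheet allows removal at any hour, as an alternative to contacting the facility. Sections 4.2.3.3.1, 4.2.4.3 and 4.2.4.4 do not ask when a patch came off.

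**Step 2: treatment window.** Application is hour 0, planned removal hour 48 and reading hour 96. The site is bare for 96 − 48 = 48 hours. The two topical corticosteroid bars differ in length (24 hours in Section 4.1.1.1.2, one to two weeks on the sheet), but both are tied to the test date. The sheet itself says that at least 72 hours are needed for allergic reactions to develop fully, so the bare period includes time when a reaction is still developing.

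**Step 3: checks.** Compliance is confirmed at Visit 1 (Section 4.2.4.2.2). Visits 2 and 3 describe removal, scoring and sign-out, with no question on creams or steroids. Question 50(m) on steroids covers the past month and is answered before the patch is applied, so it cannot capture later use.

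**Step 4: size.** Inputs are 719 residents aged 12 or older in Area 3 (Section 6.1.1, Table 2), a 65% response, 50% women and 9.5% prevalence (Section 6.1.1).

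- Women in Area 3: 719 × 0.65 × 0.5 = 233.7, which reproduces the protocol's 234.
- Expected positives: 234 × 0.095 = 22.2, taken as 22, and 22/234 = 9.40%.
- Cost of one missed reaction: 1/234 = 0.43 percentage points.

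With k true positives read as negative, observed prevalence is (22 − k)/234. The values of k are assumed.

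| k | Observed prevalence |
|---|---|
| 1 | 21/234 = 8.97% |
| 3 | 19/234 = 8.12% |
| 5 | 17/234 = 7.26% |
| 6 | 16/234 = 6.84% |

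Six of 22 (27%) must be lost before the figure falls below 7%, the lower end of the range in Section 6.1.1.

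**Step 5: can scoring repair it?** Consider setting aside compromised sites only when they read negative.

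- If three missed positives are set aside, 19/234 = 8.12% becomes 19/231 = 8.23%. This recovers 0.11 of the 9.40 − 8.12 = 1.28 points lost.
- If nine true negatives are set aside, 22/234 = 9.40% becomes 22/225 = 9.78%. This is an upward shift of 0.38 points where there was no error.

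Dropping flagged sites whatever their score is not a correction either. If three flagged sites were all correctly positive, dropping them would give 19/231 = 8.23% instead of 9.40%. Prevention on the sheet does most of the work, and flagging shows how many sites are uncertain.

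**The case against.** The case on the other side has real force.

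- **A missing patch would be noticed.** Removal is the one clinical step of Visit 2, and the sign-out nurse checks that the visit's components are complete. This stands, but seeing that a patch is gone does not give the hours of contact.
- **The call is already compulsory for severe itch or burning.** This is true and covers much of the risk. The following paragraph weakens it by making contact optional for severe or painful itching.
- **A painful site is probably reacting and may still read positive.** This stands. A false negative is possible, not certain.
- **Keeping the area dry discourages creams.** It may, but the item speaks of perspiration, showers and baths and does not bar creams.
- **The appendix is headed as preliminary and the medical-test CRF pages are not shown.** A removal-time field may exist. The conflicting instruction and the missing line on creams are nevertheless in the participant's sheet as written.

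A reader might also draw stronger conclusions that the text does not support. One is that a compromised site must be entered as an ordinary negative. The negative/positive scale has no code for an invalid test, but Section 6.4 allows missing values as a separate category, so that entry is possible, not forced. Another is that the site is open to creams for most of the 96 hours. Until about hour 48 the patch ordinarily covers it. A third is that the sheet invites early cortisone. That line concerns reactions lasting weeks, well after the reading.

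**Conclusion.** The point holds as a minor design flaw. The sheet contradicts the protocol's rule on contact and removal, and the bars on corticosteroids and creams leave out the roughly 48 hours before the reading. No described step records either event. The possible consequence is a downward bias in nickel and cobalt sensitivity prevalence.

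Its size cannot be estimated from the protocol and is probably small: 0.43 points per missed reaction among 234 Area 3 women, with every count of missed reactions assumed. The 7% used for scale is a limit of sampling precision, not a threshold for validity. The conclusion assumes that no unseen CRF page already collects removal time and site treatment. If one does, the conflict in the sheet and the gap in the bars remain, but the recording point falls away.

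**What to change.** 1. **Sheet, removal.** Keep self-removal for safety, but require a call to the facility and a noted removal time.
2. **Sheet, 96-hour list.** Add: no corticosteroid, cream or ointment on the test site until after the Visit 3 reading, unless medically needed, in which case report it.
3. **CRF, Visits 2 and 3.** Record contact hours and any site treatment or systemic steroid use since application.
4. **Analysis.** Keep the scored result in the main analysis. Flag every site with contact under 46 hours or with treatment, whatever its score, and report prevalence with and without flagged sites. Do not set aside negatives only, because that rule depends on the outcome and pushes prevalence upwards.

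The cost is a few lines on a sheet still headed as preliminary, two CRF entries at existing visits and one extra line of results. A participant with a sore site is asked to wait up to 48 hours after removal before using cortisone cream, unless it is medically needed sooner. The change has to be made before fieldwork starts.

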3.2.2.3.2 Skin sensitivity

Finally, skin sensitivity to nickel and cobalt also will be assessed. Long-term exposure to both nickel and cobalt contaminated dust has been shown to result in allergic sensitization leading to an increased incidence of allergic contact dermatitis. While primary allergic contact dermatitis has a good medical prognosis, continued exposure to the putative allergen may lead to chronic forms of dermatitis sites, such as the hands (Christensen, 1990; Schubert, 1990). Contact allergy is never inborn, although there may be some genetic factors that play a role in the development of the allergy (Menne and Neiboer, 1989). Following chronic exposure, sensitization to these metals can often occur, at which point the hypersensitivity is likely lifelong. Studies of the prevalence of delayed type hypersensitivity reactions/allergy to nickel in the general population have shown a prevalence range of 8% to 11% in females and 1% to 2% in males (Nielsen and Menne, 1993; Peltonen, 1979). More recently, considerably higher prevalence rates have been reported in the northern regions of Norway and Finland, namely, 27.5% to 39% of females (Smith-Sivertsen et al., 1999) and 5% of males (Smith-Sivertsen et al., 1999).

The prevalence of nickel allergy found in selected clinical populations referred for patch testing has shown a uniform prevalence of 14.3% (Marks et al., 1998, 1999, 2000, 2001) the prevalence for cobalt has been in the range of 6.8% to 9%. The marked difference between genders appears to be due to differences in the prevalence of ear piercing and the use of jewelry (Nielsen and Menne, 1993; Smith-Sivertsen et al., 1999; Smith Sivertsen et al., 2002). Based on the classification of both nickel and cobalt as CoCs and the clear relationship between chronic exposure to these metals and their dermatologic effects, the present study will include a skin patch test to assess sensitization to both nickel and cobalt.

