3.2.2.5 Validation

The individual medical tests described above have been included both for their utility in measuring general health and health conditions associated with exposure to the CoCs, as well as for purposes of validation. That is, specific medical tests also can be used as objective measures to validate reported medical health information from the health

questionnaire that is subjective in nature (Moffat et al., 2000; Smith- Sivertsen et al., 2000).

Medical tests that will serve as validators in this study include:

- Bilirubin test: validates the jaundice question in the questionnaire,
- Plasma cotinine test: validates recent smoking history question in the questionnaire,
- Serum TSH and fT4 test: validates thyroid condition questions in untreated individuals,
- ECG test: validates history of heart attack question in the health questionnaire,
- CO breath test: validates recent smoking history question in the health questionnaire,
- FEV1/FVC/PEFR tests: help to validate chronic bronchitis, emphysema, chronic obstructive pulmonary disease, asthma and other respiratory questions from the health questionnaire, and
- Skin patch tests: validates contact dermatitis question from the health questionnaire.

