6.1.1 Power calculations for the health questionnaire

Power was calculated based on the primary objective of the study which is to characterize the current health of residents in Port Colborne using a comprehensive health assessment questionnaire and medical testing. As mentioned previously, a stratified sampling strategy will be applied to recruit individuals from five geographical areas. The sample size of the Health questionnaire and medical tests was calculated by determining the number of individuals needed to measure the prevalence of selected health conditions with sufficient precision both within the Rodney Street Area, and the remainder of Port Colborne. Specifically, the sample size of 1,000 was selected to ensure that a 5% prevalence of asthma could be measured within an accuracy of 2% 16 times out of 20, and that the prevalence of nickel sensitivity estimated at 9.5% among women could be measured within 7% and 13% 16 times out of 20 (see Table 1 below).

Table 1: Sample Size Needed to Compare Disease Prevalence Rates (Proportions)

Health Condition	Anticipated Prevalence	Prevalence Range Permitted**	Subjects needed in Area 3	Subjects needed in remainder of Port Colborne	Minimally detectable Odds Ratio*
Asthma	5%	4-6%	418	777	2.0
Asthma	5%	3-7%	160	193	3.2
Asthma	5%	4.5%-5.5%	699	2662	1.7
Cancer	0.5%	0.4-0.6%	811	5630	3.4
Nickel Sensitivity (females)	9.5%	8%-11%	370	607	1.8
Nickel Sensitivity (females)	9.5%	7%-13%	181	223	2.4

* Comparison of prevalence of disease between Area 3 and the rest of Port Colborne

**with Power of 80% and an alpha error of 5%

Assuming that there is a response rate of 65%, and that 50% of residents in the region are female, there will be 234 female participants in the Rodney Street area and a remaining 251 female subjects in the rest of Port Colborne. This will enable nickel sensitivity to be measured with sufficient precision as outlined in the table above. Moreover, when supplemented with data obtained from males, there will be sufficient precision to measure the prevalence of asthma within an accuracy of 2% in both sexes (see Table 1). It is important to note that due to the rarity of cancer, the health questionnaire is unable to measure the prevalence of cancer in Port Colborne with sufficient precision. The evaluation of this health outcome will be addressed in a subsequent research protocol.

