Comparison of the Mean Levels of Selected Biological Measures, by Sampling Areas,
CHAP Comprehensive Health Questionnaire, Fall 2002

	Area 3	Areas 1, 2, 4, 5	Total for Port Colborne	p-value [†]
	Mean (s.d)*	Mean (s.d)	Mean (s.d)*	
Haemoglobin				
White Blood Cell Count				
Red Blood Cell Count				
Haematocrit				
Mean Cell Volume of Red Cells				
Mean Hemoglobin Concentration of Red Cells				
Platelet Count				
Red Cell Distribution Width				
Mean Platelet Volume				
Differential Leukocyte Count				
Bilirubin				
Creatinine				
Plasma Cotinine				
Plasma Screen for Concentration of TSH				
Blood Urea Nitrogen				

[†] p-value is based on an ANOVA for comparing the means between Area 3, and Areas 1, 2, 4, and 5; after adjusting for difference in the age and sex distribution of the two populations.

* s.d. = standard deviation

Table 8.
Comparison of the Non-Specimen Tests Among Participants, by Sampling Areas,
CHAP Comprehensive Health Questionnaire, Fall 2002

	Area 3	Areas 1, 2, 4, 5	Total for Port Colborne	p-value [†]
	Mean (s.d) [*]	Mean (s.d)	Mean (s.d.)	
Calculated BMI				
Electrocardiogram	---	---	---	---
Blood Pressure				
Carbon Monoxide Breath Test				
Forced Expiratory Volume in 1 second				
Forced Vital Capacity				
Peak Expiratory Flow Rate				
Dermatology Patch: Nickel Sulfate				
Dermatology Patch: Cobalt Dichloride				

[†] p-value is based on an ANOVA for comparing the means between Area 3, and Areas 1, 2, 4, and 5; after adjusting for difference in the age and sex distribution of the two populations.

^{*} s.d. = standard deviation

Table 9.
Comparison of the Selected Measures of Chemicals Among Participants, by Sampling Areas, CHAP Comprehensive Health Questionnaire, Fall 2002

	Area 3	Areas 1, 2, 4, 5	Total for Port Colborne	p-value [†]
Chemical	Mean (s.d) [*]	Mean (s.d)	Mean (s.d)	
Nickel (Urine)				
Copper (Urine)				
Cobalt (Urine)				
Arsenic (Urine)				
Mercury (Urine)				
Lead (Blood)				

[†] p-value is based on an ANOVA for comparing the means between Area 3, and Areas 1, 2, 4, and 5; after adjusting for difference in the age and sex distribution of the two populations.

^{*} s.d. = standard deviation

Table 10.
Comparison of the Proportion of Tests Outside Normal Range for Selected Biological Measures,
by Sampling Areas,
CHAP Comprehensive Health Questionnaire, Fall 2002

	Area 3	Areas 1, 2, 4, 5	Total for Port Colborne	p-value [†]
Proportion Outside Normal Range				
Haemoglobin (normal range)				

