- Rhinitis
- Nasal Polyps
- Nasal Septal Ulceration
- Other, Please specify

19. How old were you when this was first diagnosed?

_____ Age in years
(MIN: 0) (MAX: current age)

Skin:

20. Do you have a skin condition?

- Yes
- No (Go to Q23)
- Don't Know, Refused (Go to Q23)

21. What type of skin condition do you have:

INTERVIEWER: Mark all that apply.

- 1 Dermatitis/eczema
- 2 Pigmentation change (skin darkening or lightening; "change in skin color")
- 3 Hyperkeratosis (skin thickening)
- 4 Other, Please specify

22. How old were you when this was first diagnosed?

_____ Age in years
(MIN: 0) (MAX: current age)

Cardiovascular:

23. Do you have high blood pressure? 

- Yes
- No (Go to Q25)
- Don't Know, Refused (Go to Q25)

24. How old were you when this was first diagnosed? 

_____ Age in years
(MIN: 0) (MAX: current age)

Remember, we're interested in conditions diagnosed by a health professional.

25. Do you have migraine headaches? 

Yes

No (Go to Q27)

Don't Know, Refused (Go to Q27)

26. How old were you when this was first diagnosed? 

____ Age in years

(MIN: 0) (MAX: current age)

27. Do you have heart disease? 

Yes

No (Go to Q29)

Don't Know, Refused (Go to Q29)

28. How old were you when this was first diagnosed? 

____ Age in years

(MIN: 0) (MAX: current age)

29. Have you ever had a heart attack (damage to the heart muscle)? 

Yes

No (Go to Q30)

30. Do you currently have angina (chest pain, chest tightness)? 

Yes

No (Go to Q31)

31. Do you currently have congestive heart failure (inadequate heart beat, fluid build-up in the lungs or legs)? 

Yes

No (Go to Q32)

Thyroid:

32. Do you have a thyroid condition? 

Yes

No (Go to Q34)

DK, R (Go to Q34)

33. How old were you when this was first diagnosed? 

____ Age in years

(MIN: 0) (MAX: current age)

Gastro-intestinal/Liver:

34. Do you have stomach or intestinal ulcers? 

Yes

No (Go to Q36)

DK, R (Go to Q36)

35. How old were you when this was first diagnosed? 

____ Age in years

(MIN: 0) (MAX: current age)

36. Do you have Gastroenteritis?

Yes

No (Go to Q38)

DK, R (Go to Q38)

37. How old were you when this was first diagnosed?

____ Age in years

(MIN: 0) (MAX: current age)

38. Do you have Jaundice?

Yes

No (Go to Q40)

DK, R (Go to Q40)

39. How old were you when this was first diagnosed?

____ Age in years

(MIN: 0) (MAX: current age)

Neurological:

40. Do you have Peripheral Neuropathy (numbness or tingling in fingers or toes)?

Yes

No (Go to Q42)

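### The participant sheet names a p-phenylenediamine site, but the patch's purpose, sizing and result rows cover only nickel and cobalt, and section 4.2.3.3.1 does not say which allergens are applied

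*Protocol*

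**What the plan says.** - **Participant sheet** (Appendix 10.3, section 3.2): "The p-phenylenediamine site may turn black". The next sentence explains why: "This is because the allergen is a dye; it does not represent an allergic reaction". The definite article and the word allergen present the site as part of the applied patch. The substance is named nowhere else in the text available.
- **Purpose** (section 3.2.2.3.2): "the present study will include a skin patch test to assess sensitization to both nickel and cobalt".
- **Procedure** (section 4.2.3.3.1): "A standardized ready to use patch test system, the TRUE test, will be employed". Nickel and cobalt appear there only in a remark on the system's accuracy. There is no list of allergens and no restriction, and the positive/negative scoring rule is not tied to an allergen.
- **Sizing** (section 6.1.1): the target is that "the prevalence of nickel sensitivity estimated at 9.5% among women could be measured within 7% and 13" per cent, 16 times out of 20. Cobalt is not sized.
- **Results** (section 6.5.1, mock Tables 8 and 11): the patch rows are nickel sulfate and "Dermatology Patch: Cobalt Dichloride".
- **Validation** (section 3.2.2.5): "Skin patch tests: validates contact dermatitis question from the health questionnaire". The matching option in the skin part of the questionnaire (Appendix 10.1, question 21) is "Dermatitis/eczema", with no cause attached.

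**The concern.** The sheet is the only place that names a substance on the skin beyond the two metals, and the section that should settle the matter is silent. Participants are a random community sample from age 12, not patients referred for patch testing. The sheet's own side-effect list includes return of an old rash, marks that are occasionally permanent, infection, very rarely a new allergy, and extremely rarely a systemic reaction. For nickel and cobalt those risks serve a stated outcome. For any further allergen the protocol states no specific use. It also leaves open whether such a site would be scored and returned, although the sheet promises participants their patch results.

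**Working it through.** This is a question of consistency, so most of the check is a comparison of the text. The arithmetic only confirms what the sizing rests on and how many people are involved.

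**1. The plan's own patch sizing.** Inputs from section 6.1.1: prevalence p = 0.095, range 7% to 13% (lower half-width d = 0.025), confidence 16 in 20 = 80% (z = 1.2816), and populations of 16,355 in total and 719 in Area 3 (Table 2).
- n0 = z² p(1 − p)/d² = 1.6424 × 0.085975 / 0.000625 = 226.
- Remainder of the city: N = 16,355 − 719 = 15,636. With finite population correction, 226 / (1 + 225/15,636) = 223. Table 1 prints 223, so it reproduces.
- Expected women in Area 3: 719 × 0.65 × 0.5 = 233.7. The protocol states 234, so it reproduces.

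The same formula with N = 719 gives 172 for Area 3, where Table 1 prints 181; nothing here depends on that entry. The sizing uses nickel prevalence alone, and the list of allergens on the strip does not enter it.

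**2. Two readings of the sheet.**

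| | Left-over product wording | A wider strip is intended |
|---|---|---|
| Textual support | Appendix 10.3 is headed as preliminary and departs from the rest of the protocol elsewhere | The sheet states the site as fact; section 4.2.3.3.1 does not rule it out |
| People exposed to p-phenylenediamine | 0 | About 970 to 1,000, less patch exclusions |
| What is wrong | Participants are told of an allergen they do not receive | An allergen is applied with no specific stated use |

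The upper figure is the target sample of 1,000. The lower comes from section 6.1.1: (234 + 251) women at 50% female gives 485 / 0.5 = 970. The exclusions in section 4.1.1.1.2 reduce both by an amount the protocol does not give. It gives no reaction rates either, so no event counts can be derived.

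**3. Evidence that the sheet is unreconciled.** It warns of hazardous preservatives in the urine container, while the metal-test table in Appendix 10.5 requires none. It bars topical corticosteroids for one to two weeks, where section 4.1.1.1.2 says 24 hours. It puts a seafood ban under the patch instructions, although Appendix 10.5 attaches that ban to the arsenic test. This makes left-over text plausible but does not prove it.

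**4. Does another section resolve it?** Section 3.2.2.3.2 gives the purpose but does not list what is applied. Section 3.2.2.5 gives the patch tests a use not confined to metals, but never links it to further allergens. No section shown says which allergens are applied.

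**The case against.** The strongest reply is that this is one stray sentence in a draft handout. The sheet has other mismatches, and read as a whole the protocol makes the purpose clear: section 3.2.2.3.2 names the two metals and section 4.2.3.3.1 defends the system only for them. That stands to the extent that left-over text is a real possibility, in which case exposure is nil. It does not remove the contradiction, because purpose is not the same as what is put on the skin and a ready-to-use system may carry more than its users need.

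A second reply is that missing mock-table rows prove little. This is right. Free thyroxine has no row in Tables 7 and 10, cadmium has none in Tables 9 and 12, and urinalysis has none at all, yet all are measured. The absent row is supporting detail only.

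A third is that validating the contact dermatitis question could justify a wider panel. It could be argued, but the protocol does not argue it, and the questionnaire option names no cause.

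A reader might infer more: that a third allergen will certainly be applied, or that participants are not told of it at consent. The documents support neither. The first depends on which reading is true. The second cannot be checked, because the consent forms are not in the text available, and section 4.4 requires them to cover procedures and foreseeable risks.

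**Conclusion.** The contradiction is real and lies within the protocol: the sheet names a p-phenylenediamine site, the purpose, sizing and patch rows concern nickel and cobalt (the sizing nickel only), and section 4.2.3.3.1 does not limit what is applied. The number exposed to the extra allergen is either 0 or up to about 1,000 residents from age 12, less patch exclusions. The text does not show which, so confidence that anyone would be exposed can only be moderate. The wording needs correcting on either reading.

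A reader might also infer that the nickel or cobalt results are compromised. They are not: no objective, estimate, sample size or precision figure changes. The case for acting rests on participant protection and a clear procedure, which makes this a point that should be fixed before fielding rather than one that threatens the analysis. It rests on no outside knowledge of what the commercial strip contains.

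**What to change.** State in section 4.2.3.3.1 that only nickel sulfate and cobalt dichloride are applied, and order the patch material to match. If the ready-to-use system cannot be limited in this way, which the documents do not tell us, state that only the smallest TRUE strip holding both metals is used and name the other allergens on it. Delete the p-phenylenediamine text from Appendix 10.3 unless that allergen is on the strip used.

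The cost is a wording change in two places and possibly a different patch order before fielding. If the sentence is left-over text, the cost is the wording alone. Subjects, visits, exclusions, outcome definitions and sample size stay as they are.
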